12.2.7. Laboratory Assessments

Subjects will be instructed to attend each of their study visits (except Screening) in a fasted state, and subjects should remain fasted until their blood samples have been collected. At each visit, the Investigator or designee will verify that the subject has fasted for at least 8 hours and record fasting status in the source and CRF. If the subject reports having eaten (water is permitted) within 8 hours, the Investigator or designee will document accordingly in the source and CRF and remind the subject that fasting is required prior to all study visits.

Blood samples for serum chemistry and hematology will be collected at every visit as detailed in the Schedule of Study Procedures ([Section 7.1.2](#)). The number and volume of samples to be collected at each visit will be detailed in the laboratory manual.

Full instructions concerning the number and type of samples to be collected at each visit, the required sample volumes, sample collection methods, sample processing, labeling, and shipping will be provided by the central clinical laboratory in a study specific laboratory manual. All necessary collection supplies will be provided by the central laboratory and will be appropriately assembled for the specific evaluations required at each visit.

All subjects with laboratory tests containing clinically significant abnormal values are to be followed regularly until the values return to normal ranges; until a valid reason, other than

investigational product-related AE, is identified; or until further follow up is deemed medically unnecessary.

Laboratory samples will be stored for a maximum of up to 1 year after the end of the study (depending on stability) in the event that retesting is required, and destroyed after 1 year if not analyzed.

The list of laboratory analytes to be tested is shown in Table 11, and the normal reference ranges for liver biochemistries are shown in [Appendix C](#).

Table 11: List of Laboratory Analytes to be Tested

Laboratory Assessment	Analyte
Serum Chemistry	Albumin, blood urea nitrogen (BUN), creatinine, direct bilirubin, total bilirubin, aspartate aminotransferase [AST, SGOT], alanine aminotransferase [ALT, SGPT], ALP, GGT, electrolytes [calcium, chloride, potassium, sodium], glucose, total protein, and blood lipids (total cholesterol, LDL, HDL and very low density lipoprotein [VLDL] fractions and triglycerides [TG]), magnesium, phosphorus, bicarbonate, unconjugated (indirect) bilirubin, conjugated (direct) bilirubin, free fatty acids
Hematology	Hemoglobin, hematocrit, white blood count with differential, neutrophils, lymphocytes, monocytes, eosinophils, basophils, platelets, red blood cell count (including MCV, MCH, MCHC)
Coagulation	Prothrombin time (PT), partial thromboplastin time (PTT), international normalized ratio (INR)
Urinalysis	pH, specific gravity, total protein, glucose, ketones, bilirubin, blood, microscopic exam, urobilinogen, albumin, creatine, leucocytes, nitrates, albumin/creatinine ratio (if positive)
Biomarkers of Hepatic Fibrosis and/or Inflammation	IgM, C-reactive protein (CRP), TNF- α , FGF-19, CK-18, ELF, and others as determined during course of study
Genetics	DNA including single-nucleotide polymorphisms (SNPs) that may be involved in PBC; RNA
Blood Sample for Future Analysis	PBC autoantibodies and other cytokines and interleukins TBD
Other	OCA (parent and conjugates [glyco and tauro], OCA-glucuronide) and C4

The Investigator should manage subjects with clinically significant lipoprotein abnormalities using local standard of care procedures as appropriate after assessing the individual subject's total cardiovascular risk profile.

Urine-based β -hCG pregnancy tests will be performed in female subjects of childbearing potential per protocol specified visits. If a urine pregnancy test is positive, a serum pregnancy

test must be performed to confirm the result. If positive, the Sponsor must be notified and the subject will be followed, as outlined in [Section 12.1.11](#) through pregnancy outcome.

MELD scores, Child-Pugh score, and MRS will be calculated at screening, and at quarterly (MELD and Child-Pugh scores) or semi-annual (MRS) visits based on serum chemistry and coagulation.

13. STATISTICAL METHODS

A statistical analysis plan (SAP), providing details about the specific planned analyses and hypothesis tests, will be prepared and approved by the Sponsor and its designees prior to the first interim analysis, propensity score determination, and unblinding of the double-blind subject treatment assignments.

13.1. Efficacy Analysis

13.1.1. Analysis Populations

The following subject populations will be evaluated and used for presentation and analysis of the data:

- The Intent-to-Treat (ITT) Population will include all randomized subjects who receive any amount of investigational product (OCA or placebo). The ITT Population will be the primary population used for efficacy analyses. Treatment assignment will be based on the randomized treatment.
- The Per Protocol (PP) Population will include all ITT subjects who do not have any major protocol violations that potentially affect the efficacy conclusion. Treatment assignment will be based on the randomized treatment.
- The Safety Population will include all subjects who received any amount of investigational product (placebo or OCA). The Safety Population will be the primary population used for safety analyses. Treatment assignment will be based on the treatment actually received.
- The PK Population will include all OCA subjects who have at least one confirmed fasted analyzable sample. Subjects must have been fasting for approximately 8 hours prior to the visit and must not have any major protocol deviations that potentially affect exposure levels. The PK population will be used for OCA PK analyses.
- The Overall Historical Control Population will include subjects from the United Kingdom (UK) -PBC Group and Global PBC Study Group databases with demonstrated comparability to randomized subjects in this clinical study (747-302) with respect to both subject characteristics and disease progression.
- The UK-PBC Historical Control Population will include subjects from the UK-PBC Group databases with demonstrated comparability to randomized subjects in this clinical study (747-302) with respect to both subject characteristics and disease progression.

- The Global PBC Historical Control Population will include subjects from the Global PBC Study Group database with demonstrated comparability to randomized subjects in this clinical study (747-302) with respect to both subject characteristics and disease progression.

13.1.1.1. Comparability of Historical Controls

Utilization of both historical control/observational databases (UK-PBC and Global PBC Study Group), with more than 6000 subjects each, allow for a rigorous subject level meta-analysis. The historical databases include long-term follow up, detailed subject-level information such as baseline clinical characteristics, longitudinal liver biochemistry, and long-term outcomes, and span a broad range of subject characteristics that may influence disease (disease state, age, gender, and regional differences in standard of care). Historical controls from both databases will be chosen based on the same study inclusion/exclusion criteria. Propensity score matching method will be utilized to select historical controls that match the treated subjects using available covariates. The adequacy of matching will be assessed by statistical methods described under [Section 13.1.8](#).

13.1.2. Determination of Sample Size

The target population is subjects who are at higher risk of liver-related clinical complications. Eligible subjects will have a diagnosis of PBC with bilirubin levels $>ULN$ and $\leq 5x ULN$ and/or $ALP > 3 \times ULN$. The following assumptions were used in sample size calculations:

- Exponential survival curves, placebo survival estimate of 0.6 at 8 years with a hazard ratio of 0.60, and total study duration of 10 years (from first subject enrolled), allowing for 4 years of subject accrual and 6 years of follow up.
- Subjects will be randomized in a 1:1 ratio to placebo or OCA.
- The 2 groups will be compared using a 2-sided log rank test at the 5% level of significance.
- Two interim analyses and one final analysis are planned. The first interim analysis will be performed when 50% of the target events are accrued and the second interim will be performed when 75% of the target events are accrued.
- A dropout rate of 10% is assumed

Based on the randomization ratio, significance level, and assumed hazard ratio, a total of 127 events (both groups combined) will provide 80% power to demonstrate a statistically significant difference between OCA and placebo on time to liver-related outcomes, including all-cause mortality.

In addition, based on the remaining assumptions stated above, it is estimated that approximately 428 subjects will be enrolled to attain 127 events.

13.1.2.1. Sample Size Monitoring

Conducting a long-term outcomes study given the low disease prevalence, relatively slow disease progression, and ethical considerations, which in combination will impact recruitment and event rates, is inherently difficult. As stated in ICH E9, in long-term trials there is an

opportunity to check the assumptions that underlay the original design and sample size calculations. The power stated above depends on the total number of events. Thus, the overall survival function can be estimated without unblinding.

Therefore, the aggregate event rate and sample size based on recruitment and retention will be evaluated in a blinded manner quarterly. This evaluation will determine if any increases in number of subjects are required in order to obtain a total of 127 adjudicated events for the final analysis in the combined groups. Specifically, the pooled number of events will be available during the study in a blinded manner, without any knowledge of the comparative efficacy in the treatment groups. This method for evaluating the sample size does not inflate the type I error rate. Additional subjects may be enrolled as appropriate.

13.1.3. Primary Efficacy Analysis

The primary efficacy endpoint will be the time to first occurrence of one of the following post-randomization:

- Death (all-cause)
- Liver transplant
- MELD score ≥ 15
- Hospitalization (as defined by a stay of 24 hours or greater) for new onset or recurrence of:
 - Variceal bleed
 - Hepatic encephalopathy (as defined by a West Haven score of ≥ 2)
 - Spontaneous bacterial peritonitis (confirmed by diagnostic paracentesis)
- Uncontrolled ascites (diuretic resistant ascites requiring therapeutic paracentesis at a frequency of at least twice in a month).

The primary efficacy analysis will compare OCA to placebo with respect to the primary efficacy endpoint using the ITT population. Only adjudicated events will be included in analyses. The 2 treatment groups will be compared using the log rank test stratified by the randomization stratification factor. Kaplan-Meier (KM) estimates of the distribution of the time-to-event will be tabulated and graphed by treatment group. The tabulation will include the KM estimate of the medians and corresponding 95% confidence intervals (CIs), if the medians can be estimated. The number and percent of subjects censored and with events will be presented. The hazard ratio and 95% CI will be determined based on a Cox regression model stratified by randomization strata to estimate the magnitude of the effect. The same analyses for primary efficacy endpoints will be performed for PP population as a sensitivity analysis.

13.1.4. Key Secondary Efficacy Analyses

The key secondary efficacy endpoints will compare OCA to placebo on the following:

- Time to first occurrence of MELD score ≥ 15
- Time to liver transplant or death (all-cause)

- Change from Baseline in total bilirubin at end of study
- Change from Baseline in ALP at end of study

The key secondary efficacy analyses will compare OCA to placebo in the ITT population with respect to the key secondary efficacy endpoints. Only adjudicated events will be included in time-to-event analyses. The comparison (hypothesis testing) will be conducted as specified in [Section 13.1.10](#) in a sequential closed testing gate-keeping procedure, provided that the primary efficacy endpoint comparison is statistically significant in favor of the OCA treatment group. If the primary comparison is not statistically significant then comparison of the secondary endpoints will be considered as descriptive and exploratory. This procedure controls the study-wise type I error.

The 2 treatment groups will be compared using the same methodology as specified for the primary efficacy analysis ([Section 13.1.3](#)). The same analyses for key secondary efficacy endpoints will be performed for PP population as a sensitivity analysis.

Analyses of change from Baseline to end of study in ALP and total bilirubin will be compared between treatment groups using analysis of covariance (ANCOVA) with change from Baseline as the dependent variable including treatment group and randomization stratification factor as fixed effects and the Baseline values as a covariate. The same analysis will be carried out using percentage change from Baseline as the dependent variable.

Descriptive statistics of the laboratory values will be summarized by treatment group. The results, change from Baseline, and percentage change from Baseline values as well as estimates of least-square means, standard errors, and 95% CIs will be presented by treatment group. Estimates of the mean difference between treatment groups, the standard error of the difference, and 95% CI of the difference will be presented.

13.1.5. Additional Secondary Efficacy Analyses

The following time-to-event secondary efficacy analyses will compare OCA versus placebo using the ITT population:

- Time to each component of the primary efficacy endpoint (except MELD score ≥ 15 which is captured above)
- Time to development of varix/varices
- Progression to cirrhosis
- Time to occurrence of HCC
- Time to liver-related death
- Time to liver-related death or liver transplant
- Time to liver-related death, liver transplant, or MELD score ≥ 15

The same analysis methodology as used for the primary efficacy analysis will be used for these secondary efficacy analyses. Similar endpoints, where available, will be analyzed to compare OCA to historical controls as described below in [Section 13.1.8](#).

Analyses of changes in liver biochemistry (GGT, ALT, AST, conjugated bilirubin, albumin, and INR) will be summarized and analyzed using the same methodology as specified in [Section 13.1.4](#) for the key secondary analyses of change in ALP and total bilirubin.

Progression to cirrhosis will be assessed in the subset of subjects considered noncirrhotic at Baseline using available medical history, clinical, and laboratory assessments as well as baseline TE, where available. Specifically, subjects with no clinical, laboratory, or radiological evidence of cirrhosis at baseline and/or a TE liver stiffness of <16.9 kPa ([Corpechot 2012](#)) will be considered noncirrhotic (See [Section 9.7.3.1](#)). Progression to cirrhosis will be assessed by the development of clinical, laboratory, or radiological evidence of cirrhosis and/or when liver stiffness increases to ≥ 16.9 kPa during the study in which case histological progression to cirrhosis should be confirmed by biopsy unless not medically indicated. Using this definition for progression to cirrhosis, the percentage of noncirrhotic subjects progressing to cirrhosis during the treatment period will be summarized by treatment group and compared using a Cochran–Mantel–Haenszel test stratified by the randomization stratification factor.

For those subjects enrolled in the biopsy substudy (defined in Addendum 2) progression to cirrhosis identified by the above criteria and improvement in fibrosis/cirrhosis will be confirmed by paired biopsy. Analyses for the histological assessment conducted as part of the biopsy substudy are defined in Addendum 2).

Analyses of changes in MELD score, Child-Pugh score, MRS, IgM, CRP, TNF- α , FGF-19, CK-18, C4, and ELF score will be summarized and analyzed using the Wilcoxon Rank Sum Test to compare treatment groups. The median differences and 95% CI of the median differences between treatment groups will be constructed using Hodges-Lehmann estimate. If the median differences between treatments are not symmetrical around the median, the Sign Test may be used.

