8.4.2. Reasons for Mandatory Discontinuation of Investigational Product

8.4.2.1. Liver Transplantation

Subjects who undergo a liver transplant during the course of the study must discontinue investigational product and discontinue the study visit schedule. However, these subjects should be encouraged to consent to the semiannual telephone contact and/or continued record review only to allow for secondary outcome events data to be collected.

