13.1.7. Pharmacoeconomic and Health Outcomes Endpoints

Sufficient data will be collected on resource utilization and quality of life to undertake cost-effectiveness analyses that are relevant to the major countries taking part in this study. Resource utilization data on hospitalizations, healthcare provider visits, and medications will be combined with appropriate national unit costs to calculate a cost per patient per year in the study.

Quality of life data from patient-reported outcomes measures will be combined with survival data to calculate quality adjusted time in the study per patient. Cost-effectiveness analyses will report the incremental cost per major clinical outcome averted, liver-related death averted, life-year gained and quality-adjusted life year gained, including OCA as part of usual care versus usual care without OCA. Analyses will be conducted within the study and using a lifetime perspective. A separate economic analysis plan will be prepared and reported separately from this protocol.

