13.1.9.1. Time to Event Endpoints

For the time to event analyses, subjects who do not experience an event will be censored at the time of their last contact. Subjects with no data after randomization will be considered to have an event on Day 1 (first day of investigational product dosing).

For analyses of the percentage of subjects with an event, subjects with no data after randomization will be considered to have an event.

All time to event endpoints include only adjudicated events. Sensitivity analyses may consider all events regardless of adjudication. Events with discrepant adjudication will be analyzed using both results.

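### Kaplan-Meier with competing deaths censored overstates the incidence of secondary endpoints that do not include all-cause death

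*Protocol*

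**What the plan says.** Section 13.1.3 sets the primary method: a stratified log-rank test, a stratified Cox model, and a description of event times in which "Kaplan-Meier (KM) estimates of the distribution of the time-to-event will be tabulated and graphed by treatment group". Section 13.1.9.1 gives one censoring rule for all time-to-event analyses: "subjects who do not experience an event will be censored at the time of their last contact". It makes no exception for a subject who has died of something other than the analysed event.

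Three sections extend this method beyond the primary endpoint:

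- Section 13.1.5 states "The same analysis methodology as used for the primary efficacy analysis will be used for these secondary efficacy analyses". The endpoints listed there include each remaining primary component, varices, HCC, "Time to liver-related death", and two composites that combine liver-related death with transplant, one of them also with MELD ≥15.
- Section 13.1.4 applies the primary methodology to time to MELD ≥15, which is the first key secondary endpoint in the testing order of section 13.1.10.
- Section 13.1.8 prescribes Kaplan-Meier again for five outcomes against historical controls. Three of them do not include all-cause death: liver-related death, transplant, and transplant or liver-related death.

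On transplant, section 8.4.2.1 says "Subjects who undergo a liver transplant during the course of the study must discontinue investigational product and discontinue the study visit schedule". It then encourages consent to telephone contact or record review so that secondary outcome data can still be collected.

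**The concern.** For the primary endpoint, Kaplan-Meier is sound with respect to death and transplant because both count as events. It is not sound for an endpoint that leaves out all-cause death. A subject who dies of a non-liver cause cannot later have a liver-related death, a variceal bleed or HCC. Censoring that subject at death lets Kaplan-Meier act as if the event could still happen. One minus Kaplan-Meier then estimates the incidence in a setting where competing deaths do not occur (and only if the two risks are independent), not the proportion of subjects who actually have the event.

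At stake are the absolute risks that readers will take from the curves and tables for stated secondary objectives in section 6.2: the components, liver-related death and HCC. The distortion grows with follow-up, and follow-up here is planned at 6 to 10 years.

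**Working it through.** **1. The plan's own figures.** Section 13.1.2 gives placebo survival of 0.6 at 8 years, a hazard ratio of 0.60, 4 years of accrual, 6 further years of follow-up, and 10% dropout.

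- Placebo hazard of the composite: −ln(0.6)/8 = 0.0639 per year. OCA: 0.60 × 0.0639 = 0.0383 per year.
- With uniform accrual, the event probability by year 10 is 1 − [exp(−6λ) − exp(−10λ)]/(4λ). This gives 0.398 for placebo and 0.263 for OCA, mean 0.331.
- 127/0.3308 = 383.9, and 383.9/0.9 = 426.6, against the stated 428.

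The hazards therefore match the design. The protocol states no incidence for any component, so the split below is an assumption.

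**2. Formulas.** With constant component hazard a and competing hazard b:

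- one minus Kaplan-Meier, competing events censored: 1 − exp(−a·t)
- actual cumulative incidence: a/(a+b) × [1 − exp(−(a+b)·t)]

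**3. Placebo arm.** The first row takes competing death at 0.01 per year and a component at 0.02. The other rows split the whole composite hazard of 0.0639 into a component part and a competing part.

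| Assumption | 8 years: 1−KM vs actual | Relative excess | 10 years: 1−KM vs actual | Relative excess |
|---|---|---|---|---|
| a = 0.02, b = 0.01 | 14.8% vs 14.2% | 4% | 18.1% vs 17.3% | 5% |
| competing share 25% | 31.8% vs 30.0% | 6% | 38.1% vs 35.4% | 8% |
| competing share 50% | 22.5% vs 20.0% | 13% | 27.3% vs 23.6% | 16% |
| competing share 75% | 12.0% vs 10.0% | 20% | 14.8% vs 11.8% | 25% |

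Example, first row at 8 years: 1 − exp(−0.16) = 0.148, and (0.02/0.03) × [1 − exp(−0.24)] = 0.142. A simulation at the 50% share gave 22.6% against 20.1% at 8 years, in agreement with the formula.

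**4. OCA arm.** With the hazard ratio of 0.60 on both parts, the excess at 8 years is 4%, 8% and 12% for shares of 25%, 50% and 75%.

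**5. Difference between arms at 8 years.**

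- Hazard ratio 0.60 on both parts, shares 25/50/75%: Kaplan-Meier gives 11.3/8.3/4.6 points and the actual difference is 10.2/6.8/3.4 points. Kaplan-Meier overstates.
- Component hazards 0.02 versus 0.012, competing hazards 0.01 versus 0.04. Kaplan-Meier: 14.8% − 9.2% = 5.6 points. Actual: 14.2% − 7.9% = 6.4 points. Kaplan-Meier understates.

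The sign of the error in the difference depends on what treatment does to the competing event.

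**The case against.** The strongest reply is that little hangs on this. Section 13.1.10 makes the additional endpoints descriptive and exploratory, the primary endpoint is not touched, and counts of subjects with events are tabulated beside the curves. A SAP could add a cumulative incidence display. This stands as a limit on consequence. It does not remove the point, because the protocol names both the estimator and the censoring rule, and time to MELD ≥15 sits in the testing hierarchy, although its test is not invalidated.

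The size is also open to challenge, and fairly. The 0.064 hazard covers every first event in the composite. Under section 8.4, subjects normally stay on the visit schedule after a non-fatal outcome, so those events do not compete. A 75% competing share is therefore a high assumption. Only the earliest enrolled reach 10 years.

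A reader might infer more than the documents support:

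- *That subjects are censored at transplant.* The rule is last contact, and follow-up after transplant continues with consent. Liver-related death can still follow a transplant.
- *That the absolute benefit is always inflated.* Step 5 of the working shows that it need not be.
- *That all historical-control outcomes are affected.* All-cause death, and transplant or all-cause death, are not.
- *That the economic results inherit the error.* Section 13.1.7 says "Cost-effectiveness analyses will report the incremental cost per major clinical outcome averted, liver-related death averted", but it does not say that these counts come from Kaplan-Meier curves, and it defers to a separate economic analysis plan.
- *That the tests are invalid.* The log-rank and Cox analyses keep their meaning as comparisons of cause-specific hazards.

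**Conclusion.** The point holds for the incidence estimates in sections 13.1.4 (time to MELD ≥15), 13.1.5 and 13.1.8 wherever the endpoint does not include all-cause death: the non-fatal components, transplant, HCC, varices, liver-related death and the liver-related composites. In each arm, one minus Kaplan-Meier exceeds the actual incidence whenever competing deaths occur. That direction does not depend on the assumed rates; the size does. With constant hazards, the placebo-arm excess at 8 to 10 years is about 4–5% of the true value at the low end and about 20–25% at the high end. Transplant adds to it only where it prevents the event or ends its ascertainment. No hypothesis test, sample size or primary result changes.

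**What to change.** In sections 13.1.4, 13.1.5 and 13.1.8, replace one minus Kaplan-Meier by Aalen-Johansen cumulative incidence for the affected endpoints, and name the competing events for each:

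- non-fatal endpoints, including MELD ≥15, transplant, HCC and varices: death from any cause;
- liver-related death and its composites: non-liver death;
- transplant: a competing event only where it is not part of the endpoint and it precludes the event or its ascertainment.

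Add to section 13.1.9.1 that the censoring rule does not apply to these competing events when incidence is estimated. Keep the stratified log-rank and Cox analyses and label them cause-specific. Keep Kaplan-Meier for the primary endpoint, all-cause death, and transplant or all-cause death.

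The cost is a short text change and programming. No further randomised-trial data are needed, because deaths and transplants are already collected and adjudicated, and sample size and alpha are unchanged. For section 13.1.8, the historical databases already record all-cause and liver-related death and transplant.

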9.4. Randomization and Blinding

This study will be conducted in a double-blind, placebo-controlled manner. Allocation to one of two treatment groups (OCA or placebo) will occur on a 1:1 ratio across sites and will be stratified by UDCA treatment (yes/no) and mean baseline bilirubin categories ($>ULN/\leq ULN$), as specified by the central laboratory. The randomization will be based on a predefined randomization code (generated by the Sponsor or designee) using an interactive web response system (IWRS), which the Sponsor intends will serve as a computer-based subject registration system at Screening and Day 0. The IWRS will serve as an investigational product inventory and management system and may be integrated with the study database.

The Investigator or designee will be required to register the subject in the IWRS and may be prompted to provide subject data necessary to properly randomize and allocate the subject to treatment. A randomization number will be assigned (refer to [Section 9.5.2](#) below) and investigational product dispensing information (ie, bottle number[s]) will be provided.

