13.1.10. Multiple Comparisons/Multiplicity

The key secondary efficacy endpoints are as follows:

- Time to MELD score ≥ 15
- Time to first occurrence of liver transplant or death (all-cause)
- Change from Baseline in total bilirubin at end of study
- Change from Baseline in ALP at end of study

The hypothesis testing of key secondary analyses will compare placebo and OCA and will be conducted in a sequential closed testing gate-keeping procedure (in the order in which the key secondary endpoints are stated above), provided that the primary efficacy endpoint comparison is statistically significant in favor of OCA. If the primary comparison is not statistically significant then comparison of the secondary endpoints will be considered as descriptive and exploratory. This procedure controls the study-wise type I error.

- First (step 1) placebo and OCA will be compared with respect to the primary efficacy endpoint. If the comparison achieves statistical significance at 2-sided 0.05 level in favor of OCA group, then
- The time to MELD score ≥ 15 will be compared between placebo and OCA (step 2). If the comparison achieves statistical significance at 2-sided 0.05 level in favor of OCA group, then
- The time to liver transplant or death (all-cause) will be compared between placebo and OCA (step 3). If the comparison achieves statistical significance at 2-sided 0.05 level in favor of OCA group, then
- Change from Baseline in total bilirubin will be compared between placebo and OCA (step 4). If the comparison achieves statistical significance at 2-sided 0.05 level in favor of OCA group, then
- Change from Baseline in ALP at the end of study will be compared between placebo and OCA (step 5).

If at any step defined above the comparison is not statistically significant at the 2-sided 0.05 level then the remaining comparisons in the stated hierarchy will be considered descriptive

and exploratory. The study-wise type I error will be maintained with the above closed procedure.

Additional efficacy endpoints will be analyzed; however, hypothesis tests will be applied for descriptive and exploratory purposes only.

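### Section 13.1.5 allows an optional, data-dependent fallback to the Sign Test, which has no proper form for two unpaired randomised arms and is triggered by a condition the planned rank-sum test does not need

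*Protocol*

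**What the plan says.** Protocol Section 13.1.5 covers changes in MELD score, Child-Pugh score, Mayo Risk Score, IgM, CRP, TNF-α, FGF-19, CK-18, C4 and ELF score. These are to be "analyzed using the Wilcoxon Rank Sum Test to compare treatment groups". For estimation, "The median differences and 95% CI of the median differences between treatment groups will be constructed using Hodges-Lehmann estimate". The next sentence reads: "If the median differences between treatments are not symmetrical around the median, the Sign Test may be used". It gives no criterion for asymmetry and does not say how a Sign Test would be formed between arms.

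The design is a two-arm parallel comparison. Section 13.1.2 states that "Subjects will be randomized in a 1:1 ratio to placebo or OCA", and Section 9.4 has allocation "stratified by UDCA treatment (yes/no) and mean baseline bilirubin categories". No pairing of subjects across arms is defined in either section.

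The neighbouring analyses are adjusted. Section 13.1.4 analyses change in ALP and total bilirubin by ANCOVA, "including treatment group and randomization stratification factor as fixed effects and the Baseline values as a covariate". Section 13.1.5 extends that model to GGT, ALT, AST, conjugated bilirubin, albumin and INR. The rank-sum paragraph names neither a baseline term nor a stratification factor.

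For endpoints outside the primary and key secondary hierarchy, Section 13.1.10 states that "hypothesis tests will be applied for descriptive and exploratory purposes only".

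**The concern.** The sentence has two faults.

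First, the Sign Test counts positive and negative signs in a single set of independent differences, so it needs one sample or matched pairs. Two unpaired arms do not supply such a set.

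Second, the trigger belongs to another test. Symmetry about the median is assumed by the Wilcoxon signed-rank test for paired data. The rank-sum test does not assume it. The sentence looks as if it was carried over from a paired analysis.

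Following it would mean leaving a valid randomised comparison because an assumption that comparison never made appears to fail. The decision would be taken after looking at the data, with no stated threshold. At stake is the between-arm comparison of ten secondary scores and markers, several of which serve the Section 6.2 objective on inflammation and fibrosis.

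**Working it through.** The sentence carries no figure, so there is nothing of the plan's own to reproduce. The check takes each way of applying a Sign Test to two independent arms and asks what it would deliver.

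**Inputs.** Arms are 1:1 (Section 13.1.2). Enrolment is about 428 (Section 13.1.2), so 428 / 2 = 214 per arm. Assumed for illustration: complete data, log-normal (skewed) changes, two-sided 5% level.

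**Is the trigger relevant?** With no difference between arms and skewed changes, the rank-sum test rejected in 5.3% of 3,000 simulated trials. Skewness does not break it. There is a further problem if the condition is read literally, as concerning cross-arm differences. The difference between two independent draws from the same distribution is symmetric about zero however skewed that distribution is, and under a pure shift it is symmetric about the shift. Apart from sampling noise, such differences look asymmetric only when the two arms differ in shape, so the choice of test would itself depend on the treatment comparison.

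**What could the Sign Test be?**

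| Reading | Result under the assumptions above |
|---|---|
| Within one arm, on change from baseline | With identical arms and a common median change of 0.3, rejects 98% of the time. It tests change over time, not treatment. |
| Subjects paired arbitrarily across arms | Type I error 4.8%. One simulated dataset with rank-sum p = 0.0002 gave Sign Test p-values from 0.000001 to 0.19 over 2,000 random pairings. For a shift of 0.25, power was 71% against 87% for the rank-sum test. |
| All 214 × 214 = 45,796 cross-arm differences treated as independent | Type I error about 87% (500 simulated trials). |

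The first reading answers another question, the second is arbitrary and weaker, and the third is invalid.

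**Precision available from baseline and strata.** This is a separate matter from the error. Let s² be the single-visit variance, equal at both visits, and r the correlation between baseline and follow-up.

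- Variance of an unadjusted change: 2s²(1 − r).
- Residual variance under ANCOVA: s²(1 − r²).
- Ratio: (1 − r²) / [2(1 − r)] = (1 + r) / 2.

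At r = 0.5: 0.75 against 1.00, a 25% saving. At r = 0.7: 0.51 against 0.60, a 15% saving. Over r = 0.3 to 0.9 the ratio runs from 0.65 to 0.95. The protocol gives no correlations, so these are assumed. The formula is normal theory for raw changes, and for rank methods it is only a guide.

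The strata are relevant too. One randomisation factor is baseline bilirubin, and total bilirubin enters both the Child-Pugh score (Section 9.7.4) and the Mayo Risk Score (Section 9.7.5).

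**The case against.** The strongest reply is that little follows from the sentence. The wording is permissive, the committed analysis is a valid rank-sum test with a matching estimate and interval, and Section 13.1.10 makes these tests descriptive and exploratory. A data-dependent choice of test there inflates no error rate that the study controls. All of that stands, and it limits the weight of the point. It does not rescue the sentence, because an option that should never be exercised is better removed.

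Three stronger readings are tempting, and the documents support none of them.

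- A reader might infer that omitting baseline and strata is an error. It is not. An unadjusted rank-sum test is valid under randomisation, and the ANCOVA in Sections 13.1.4 and 13.1.5 is assigned to other variables, so nothing is contradicted. A stratified or covariate form could also properly be left to the statistical analysis plan.
- A reader might infer that the fibrosis and severity results as a whole rest on an unsuitable test. They do not. Time to MELD score ≥15 uses the stratified log-rank method, and progression to cirrhosis, which takes in liver stiffness, is compared by a stratified Cochran-Mantel-Haenszel test. Only changes in the ten listed variables are exposed, and only if the option is used.
- A reader might infer that no Sign Test could hold its level. Arbitrary pairing did hold it, at 4.8%. Its faults are a p-value that depends on the pairing and lost power. Nor does the protocol propose a within-arm test, which is only one of the readings the sentence leaves open.

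**Conclusion.** The point holds for the Sign Test sentence. It names a one-sample or paired test for an unpaired comparison and attaches a symmetry condition that the planned test does not require. If used, it would replace a valid analysis with an arbitrary or invalid one. That conclusion rests on the nature of the tests and the parallel-arm design. The simulated figures only illustrate it, under 214 complete subjects per arm and log-normal changes.

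The importance is low. The primary result, alpha, testing hierarchy, sample size and power are untouched.

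Adjusting for baseline and strata is an efficiency improvement, not a correction. The indicative variance saving is 25% at r = 0.5 and 15% at r = 0.7, on assumed correlations and normal theory.

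**What to change.** Delete the Sign Test sentence from Section 13.1.5 and keep the Wilcoxon rank-sum test with the Hodges-Lehmann estimate and 95% confidence interval. That alone removes the error.

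As an optional improvement in line with Section 13.1.4, replace the unadjusted test with a rank ANCOVA that has baseline as covariate and the randomisation strata as factors, keeping the Hodges-Lehmann difference and interval for description. A van Elteren test stratified by the randomisation factors is simpler, but it adjusts for strata only and would not recover the gain from the measured baseline value.

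The cost is wording in the protocol, carried through to the statistical analysis plan. No new data are needed, because baseline values and stratification factors are already collected.
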